## 4. STUDY POPULATION

## 4.1 Population (base)

*Patients.* Approximately 800 patients between 18 and 65 years, that apply for individual psychotherapy or psychological treatment at one of the three research locations (Schagen, Deventer, Twello), will be asked to participate in the study. *Therapists.* Therapists are psychotherapists, psychologists or psychiatric nurses that work

at the three research locations. Trainees will be excluded from the study. Approximately 50 therapists will be included in the study.

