## 4.4 Sample size calculation

Performing an a priori power analyses for multilevel analysis is complicated, because one has to have a good estimate of the variance components in advance and these are usually unknown, especially for three level models and three research conditions (de Jong, Moerbeek & Van der Leeden, 2009). An a priori power analysis was performed for two research conditions, based on the variance components of previously collected data, which resulted in approximately 4 patients per therapist, and 50 therapists participating for a power of 0.80, which is generally considered to be sufficient. However, this analysis was performed with an intended moderate effect (Cohen's d = 0.50), whereas feedback metaanalysis shows a small effect (Cohen's d=0.30). Also, in the current study we have three research conditions, which is considerably more complicated to model. The difference between the two feedback conditions is most likely smaller than d=0.30. Another thing that needs to be considered is that the effect only applies to the "not on track" group. As this group consists of approximately 25% of the total patient group and we cannot identify this group beforehand, the number of patients that need to be included in the study needs to be four times as large as the results from the a priori power analysis.

A traditional a priori power analysis was performed in G\*Power 3.0.10 for F tests with repeated measures, three research groups, three repeated measures, a power coefficient of 0.80, an  $\alpha$  of 0.05, and a correlation of 0.70 between the repeated measures. This resulted in a needed sample size of 90 not on track patients. The total sample size needed would then be 360 patients. This analysis does not take into account that patients are nested within therapists and therapists will explain part of the variance. We know from a previous study that the intraclass correlation was 0.18 at the therapist level. A rule of thumb to correct for the variance at the therapist level is to use the formula for the design effect:  $1 + (k-1)^{*icc}$ , with k being the number of patient per therapist, we would get a design effect of: 1 + 3 \* 0.18 = 1,54. This means that  $1.54^{*}360 = 554$  patients need to be included in the study. As we expect that some of the data will not be valid, the number of 600 patients was chosen as targeted *N*.

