## 5. TREATMENT OF SUBJECTS

## 5.1 Investigational product/treatment

In the ETR feedback condition, the therapist will receive feedback about the patient's progress, bases on an expected treatment response model. The ETR model is based on data collected in three different mental health care organizations in the Netherlands (de Jong et al, in preparation). Therapists receive an alert when the patient deviates from the expected track. An error bound around the expected treatment response for the patient indicates when the therapist is signals. If 75% failure boundary is crossed by the patient, the therapist receives an orange warning signal, indicating that the patient has an increased chance of treatment outcome. If the 95% failure boundary is crossed, the therapist receives a red warning signal, indicating that the patient is most like to have poor treatment outcome if he or she continues on the current track. When the patient signals orange or red, the Assessment for Signal Clients questionnaire will be administered to the patient, and the therapist will receive feedback about the scores on the ASC, in addition to the scores on the OQ-45.

In the ROM feedback condition, feedback is given in the form that most routine outcome monitoring feedback is being provided. The therapist gets a graph of the patient's progress after session 1, 3, 5, 10 and 15. In the graph, the patient's progress on the OQ-45 is monitored. The therapist receives feedback on the OQ total score, the subscale scores and the critical items.

In the control condition, therapists will receive no feedback about their patient's progress. All therapists can be in all three conditions, as randomization takes place at the patient's level.

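### The step from 360 to 554 patients uses a design effect for whole-therapist allocation, although patients are randomised individually and a therapist can have patients in all three conditions

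*Protocol*

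**What the plan says.** Protocol section 4.4 reaches its target in four steps.

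- A repeated-measures F test: "This resulted in a needed sample size of 90 not on track patients".
- Scaling up by four for the share of such patients: "As this group consists of approximately 25% of the total patient group". This gives 360.
- A clustering correction by the rule of thumb 1 + (k − 1) × ICC, with a therapist-level ICC of 0.18 from a previous study: "with k being the number of patient per therapist, we would get a design effect of" 1 + 3 × 0.18 = 1.54, hence 554.
- Rounding up to 600 for data that will not be valid.

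On therapists, section 4.1 says: "Approximately 50 therapists will be included in the study". On allocation, section 5.1 says: "All therapists can be in all three conditions, as randomization takes place at the patient's level". Section 8.2 repeats that randomisation is at the patient level and puts therapists at level three of the model. Section 6.2 describes the allocation as wholly random and names no stratification by therapist.

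**The concern.** The rule 1 + (k − 1) × ICC measures how much variance is added when everyone treated by one therapist is in the same arm, so that differences between therapists become differences between arms. In this trial one therapist's patients can fall in any of the three arms. Differences between therapists are then largely common to the arms, and the three-level model removes them from the condition contrast.

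The value of k is a second difficulty. The text defines it as patients per therapist and uses 4, which does not agree with the planned number of patients and therapists.

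At stake is the justification of the target. This step is the only stated reason for going from 360 to 554, and so the main support for 600. Sections 4.4 and 8.3 also plan a power analysis after six months that may prolong inclusion. If that analysis reuses this rule, the decision will rest on a formula that does not fit the design.

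**Working it through.** **Inputs.** From section 4.4: 90 not-on-track patients, a 25% share, ICC = 0.18, k − 1 = 3, target 600. From section 4.1: about 50 therapists. From sections 5.1, 6.2 and 8.2: patient-level, unstratified randomisation, with therapist in the model.

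**1. The plan's own figure.** 90 × 4 = 360. 1 + 3 × 0.18 = 1.54. 1.54 × 360 = 554.4, stated as 554. It reproduces.

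**2. Does k = 4 fit the definition?**

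| Patients counted | At 360 | At 554 | At 600 |
|---|---|---|---|
| All, per therapist | 360/50 = 7.2 | 554/50 = 11.1 | 600/50 = 12 |
| Not-on-track only, per therapist | 90/50 = 1.8 | 138.5/50 = 2.8 | 150/50 = 3 |

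No entry is 4. The number 4 appears in section 4.4 as patients per therapist in the separate two-condition analysis at d = 0.50 (4 × 50 = 200 patients). It also equals 600/(50 × 3), patients per therapist per arm at the target. The text does not say which, if either, was meant.

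**3. The multiplier under the actual allocation.** Take one outcome per patient, as the plan's own rule does, a random therapist intercept with ICC ρ, k patients per therapist, simple randomisation to three equal arms and no therapist-by-condition variance. The generalised least squares variance of a contrast between two arms, relative to independent patients, is

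(1 − ρ) × [1 + (k − 1)ρ] / [1 + (k − 2)ρ].

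- k = 3: 0.82 × 1.36 / 1.18 = 0.945, and 0.945 × 360 ≈ 340.
- k = 12: 0.82 × 2.98 / 2.80 = 0.873, and 0.873 × 360 ≈ 314.

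If every therapist's patients were split equally over the arms, the multiplier would be 1 − 0.18 = 0.82 (295 patients). That is a floor, because the allocation is not stratified. With 3 patients per therapist, only 3!/3³ = 6/27 = 22% of therapists would have all three arms represented.

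**4. What could inflate the number.** Let w be the therapist-by-condition variance as a share of the total, and m the patients per therapist per arm. With equal splitting, an approximate multiplier is (1 − 0.18) + m × w. The protocol gives no value for w, so the values below are assumptions.

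| w (assumed) | m = 1 (not-on-track, 150/(50 × 3)) | m = 4 (all patients, 600/(50 × 3)) |
|---|---|---|
| 0 | 0.82, 295 | 0.82, 295 |
| 0.05 | 0.87, 313 | 1.02, 367 |
| 0.18 | 1.00, 360 | 1.54, 554 |

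To return 1.54 at m = 4, w must be (1.54 − 0.82)/4 = 0.18. The therapist-by-condition variance would have to be as large as the whole therapist ICC.

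**The case against.** The strongest defence is that the step does no harm. It is offered as a rule of thumb, it errs upward under most assumptions, and a power check on observed variance is planned at six months. The protocol also expects therapists to respond differently to feedback: its secondary objectives ask whether feedback propensity and goal commitment predict outcome in the feedback conditions. Some therapist-by-condition variance is therefore plausible, and a large enough share brings back 554. Since the trial is powered on not-on-track patients, k may also have been meant to count only those, and 4 would then be slightly above the 3 expected at 600.

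Most of this stands as a limit on the point. It does not rescue the derivation. The text defines k as patients per therapist without restriction, and the ICC of 0.18 is a therapist-level correlation, not a therapist-by-condition variance. An allowance for differential response may be reasonable, but it needs its own stated value.

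A reader might also go further and put k = 12 into the same rule, which gives 1 + 11 × 0.18 = 2.98 and 2.98 × 360 = 1,073, and conclude that 600 is far too few. The documents do not support that. The rule does not apply to patient-level randomisation, so k no longer matters once the rule is dropped, and a larger k cannot be the correction.

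**Conclusion.** Section 4.4 is wrong as written on this step. The figure 554 is multiplied out correctly, so this is not an arithmetic slip. It rests on a formula for another design and on a k that does not match the protocol's own numbers.

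With patients randomised individually, the therapist ICC of 0.18 does not inflate the condition contrast. The multiplier is about 0.94 to 0.87, or about 340 to 314 patients instead of 554. This assumes simple randomisation, equal caseloads over about 50 therapists, therapist in the model, one outcome per patient and no therapist-by-condition variance. Therapist-by-condition variance would raise the figure. As an assumption, a share of about 0.18 with 4 patients per therapist per arm would be needed to return 1.54.

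Two further inferences do not follow. The step does not show that 600 is too small for clustering, because 1.54 generally over-inflates under the actual design. For the same reason it cannot be said to make the plan look more cautious about clustering than it is. Whether 90 is the right base is a separate question about the effect size and is taken as given here.

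**What to change.** Reword section 4.4:

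- Delete the 1.54 step and the figure 554.
- State that patients are randomised within therapist, so the therapist ICC of 0.18 does not inflate the comparison of conditions.
- If an allowance for clustering is wanted, base it on an explicit assumed range of therapist-by-condition variance and show the resulting multiplier.
- Say which patients are counted per therapist: all of them (about 12 at 600) or those not on track (about 3).
- Keep the target of 600 and restate what it delivers: at a 25% share, about 150 not-on-track patients, or 50 per condition.
- Name the same method for the six-month power analysis in sections 4.4 and 8.3.

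The cost is a rewritten paragraph and one cross-reference. The target, the allocation and the analysis model stay as they are.

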## 5. TREATMENT OF SUBJECTS

## 5.1 Investigational product/treatment

In the ETR feedback condition, the therapist will receive feedback about the patient's progress, bases on an expected treatment response model. The ETR model is based on data collected in three different mental health care organizations in the Netherlands (de Jong et al, in preparation). Therapists receive an alert when the patient deviates from the expected track. An error bound around the expected treatment response for the patient indicates when the therapist is signals. If 75% failure boundary is crossed by the patient, the therapist receives an orange warning signal, indicating that the patient has an increased chance of treatment outcome. If the 95% failure boundary is crossed, the therapist receives a red warning signal, indicating that the patient is most like to have poor treatment outcome if he or she continues on the current track. When the patient signals orange or red, the Assessment for Signal Clients questionnaire will be administered to the patient, and the therapist will receive feedback about the scores on the ASC, in addition to the scores on the OQ-45.

In the ROM feedback condition, feedback is given in the form that most routine outcome monitoring feedback is being provided. The therapist gets a graph of the patient's progress after session 1, 3, 5, 10 and 15. In the graph, the patient's progress on the OQ-45 is monitored. The therapist receives feedback on the OQ total score, the subscale scores and the critical items.

In the control condition, therapists will receive no feedback about their patient's progress. All therapists can be in all three conditions, as randomization takes place at the patient's level.

## 5.2 Use of co-intervention

Patients are not excluded for getting co-interventions that supplement the individual treatment. Pharmacological treatment, as well as other treatment forms are allowed. However, if individual treatment is no longer the main treatment, patients are excluded from the study (e.g. a patient starts out with individual treatment and is referred to group therapy. He or she might still see the individual therapist, but on a low frequency, the study is stopped for this patient then. Data collected up until then will still be used in analysis).

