**Study design:** A 2-year randomized controlled clinical trial on the effectiveness of feedback interventions for therapists

**Study population:** The study population consists of psychiatric patients between 18 and 65 years that apply for outpatient individual psychiatric treatment in one of the three participating treatment facilities. Patients with psychotic disorders, a current crisis, a high risk of decompensation, a current severe manic episode or insufficient mastery of the Dutch language in reading and speaking are excluded from participating in the study. Patients can have supplement treatments beside the individual treatment and stay in the study, as long as

the individual treatment remains the main treatment. Patients are excluded from the study if individual treatment is not their main treatment.

**Intervention (if applicable)**: The intervention consists of providing feedback to therapists on their patients' progress. In the outcome monitoring feedback condition the therapist gets feedback on patient progress in progress charts and tables. The progress of the patient can be viewed by the therapist at all times, by logging on to the feedback system (RequestXL), but is also actively provided by e-mail at session 1, 3, 5, 10 and 15.

In the complex feedback condition with prediction model the actual treatment course (based on the OQ scores) of the patient is compared with the predicted treatment course. The expected treatment course is calculated by a formula. The progress of the patient can be viewed by the therapist at all times, by logging on to the feedback system (RequestXL), but is also actively provided by e-mail when the patient is not progressing well. The therapist then receives an e-mail with high urgency.

In the complex feedback condition feedback is also provided on the ASC. The ASC is administered when the patient goes off track (through the 75% negative bound of the confidence interval around the predicted treatment course) and measures the therapeutic alliance, motivation, social support and life events. The ASC is combined with so called Clinical Support Tools, a set of Microsoft Word documents that provide practical tips on improving the therapeutic alliance, motivation and social support. The practical tips are based on a literature review on these topics.

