**Main study parameters/endpoints:** The primary outcome measure of the study is patients' disfunctioning on the Outcome Questionnaire. Mores specifically, the progress that the patient makes during treatment. The results will be analysed using multilevel analysis, which has the advantage of being able to handle missing data really well. Therefore, data from all patients, including those that dropped out of treatment or dropped out of the study can be used in analysis.

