## 6.1.2 Secondary study parameters/endpoints

Two follow-up measures are included in the study design: one at three months and one at six months after treatment termination or 15 sessions of treatment. Another secondary study parameter includes the percentage of treatment drop-outs in each reseach condition.

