## 6.4 Withdrawal of individual subjects

Subjects can leave the study at any time for any reason if they wish to do so without any consequences. The investigator can decide to withdraw a subject from the study for urgent medical reasons, or if the patients diagnosis or treatment is changed in such a way that the patient no longer fits the inclusion criteria of the study.

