## 6.6 Follow-up of subjects withdrawn from treatment

Patients that withdraw from treatment (drop-outs) will not be followed-up.

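### Patients who drop out or move to another main treatment stop being measured, which conflicts with the planned 3- and 6-month follow-up and may select patients differently by arm

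*Protocol*

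**What the plan says.** Section 5.2 states that "if individual treatment is no longer the main treatment, patients are excluded from the study". It gives referral to group therapy as the example and adds that "the study is stopped for this patient then. Data collected up until then will still be used in analysis". The Summary repeats the rule: "Patients are excluded from the study if individual treatment is not their main treatment". The rule has a limit: "Patients are not excluded for getting co-interventions that supplement the individual treatment", and drug treatment is permitted.

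Section 6.4 lets the investigator withdraw a patient on urgent medical grounds, and also "if the patients diagnosis or treatment is changed in such a way that the patient no longer fits the inclusion criteria". Section 6.6 says: "Patients that withdraw from treatment (drop-outs) will not be followed-up".

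Against this, section 6.1.2 makes two follow-up measures secondary endpoints, "one at three months and one at six months after treatment termination or 15 sessions of treatment". The procedure part of section 6.3 plans the same two OQ-45 measures, counted from the end of treatment or of the study. The burden paragraph of the Summary counts them from the end of treatment or session 15. None of the three names an exception. Section 6.1.2 also lists the percentage of treatment drop-outs per arm as a secondary parameter.

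On missing data, the Summary relies on multilevel analysis and says that data from all patients, "including those that dropped out of treatment or dropped out of the study can be used in analysis".

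**The concern.** There are two problems. The first is plain inconsistency: staff cannot tell from the protocol whether a drop-out or a referred patient is to be sent the follow-up questionnaires.

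The second is that these exits happen after randomisation and lie partly in the therapist's hands. Section 1 presents feedback as a way to let clinicians adjust treatment. Under section 5.1, therapists in the prediction-model arm receive orange or red warnings and the ASC scores, those in the monitoring arm receive progress graphs, and those in the control arm receive nothing. Section 6.2 says that therapists know the arm. Moving a patient to another main treatment is a plausible response to a warning. Section 4.4 expects an effect only in the roughly 25% of patients who are not on track, and warnings fall on this group.

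If exit differs by arm, the 3- and 6-month comparisons are no longer between the groups that were randomised. The primary comparison would also leave out whatever feedback achieves, for good or ill, by changing the main treatment.

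**Working it through.** **1. The passages side by side, by type of exit**

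| Exit | Rule that ends measurement | Rule that continues it |
|---|---|---|
| Treatment drop-out | 6.6: no follow-up | 6.1.2, 6.3, Summary: 3 and 6 months after end of treatment |
| Individual treatment no longer the main one | 5.2, Summary: study stops, earlier data kept | 6.3: 3 and 6 months after end of treatment or study |
| Withdrawn because treatment or diagnosis changed | 6.4 (discretionary); 6.5 uses data up to withdrawal | 6.3, as above |

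Every row has two rules, and nothing says which takes precedence.

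**2. What the planned model can recover**

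Section 8.2 specifies a three-level random-intercept, random-slope model with initial severity as covariate. If exit is explained by OQ-45 scores already observed, a likelihood-based fit uses the scores before exit validly. What it then estimates is the course had the patient stayed in individual treatment. Session scores after the new main treatment begins are not collected, so the model has no information about that course. Section 2 asks whether feedback improves patient outcomes, and does not limit the question to patients who stay in individual treatment.

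**3. Allowance for loss in the sample size (section 4.4)**

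The plan's own chain reproduces:
- 90 / 0.25 = 360
- 1 + 3 × 0.18 = 1.54
- 1.54 × 360 = 554.4, stated as 554, with 600 as target
- allowance: (600 − 554) / 600 = 7.7%, for invalid data of any kind

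No drop-out or removal rate is stated. For an assumed total loss q, 600 × (1 − q) patients remain, and keeping 554 needs 554 / (1 − q) enrolled:

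| q (assumed) | Left of 600 | Enrolment to keep 554 |
|---|---|---|
| 10% | 540 | 616 |
| 20% | 480 | 693 |
| 30% | 420 | 792 |

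For the primary analysis these are worst cases, since scores before exit are used. They apply more directly to the follow-up measures.

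**4. Illustration of selection (all rates assumed)**

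Let d be the true difference in final outcome between all randomised patients, q_F and q_C the exit shares in a feedback arm and in control, and s the amount by which those who leave differ from those who stay, in SD. The mean among stayers is the arm mean minus q × s, so the difference among stayers is d − (q_F − q_C) × s. Take d = 0.30, the small effect named in section 4.4:

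| q_F, q_C | s = +0.5 | s = −0.5 |
|---|---|---|
| 10%, 10% | 0.30 | 0.30 |
| 20%, 10% | 0.30 − 0.10 × 0.5 = 0.25 | 0.35 |
| 30%, 10% | 0.30 − 0.20 × 0.5 = 0.20 | 0.40 |

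Equal exit with equal shift gives no bias. Otherwise the error can go either way. This is a contrast of stayers. The multilevel model would remove part of the error where exit follows observed scores.

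**The case against.** The other side has several good points.

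- A reader might infer that any change of treatment removes the patient. It does not: supplementary and drug treatment are allowed, and only a change of main treatment counts, or a change after which the inclusion criteria no longer fit. This stands.
- A reader might infer that removed patients are lost to the analysis. Their scores before exit are kept under sections 5.2 and 6.5. The loss concerns later OQ-45 scores and possibly both follow-ups. This stands too.
- A reader might infer that removal does depend on arm. The protocol does not show this. The support tools described in the Summary work within the ongoing treatment, no passage names referral as the intended response to feedback, and referral can happen in the control arm. Dependence on arm is plausible, no more.
- Section 6.6 could be read as a specific exception to the general follow-up rule, and section 6.3 could mean that referred patients are followed. Both readings are possible. The protocol states neither, and under the first the selection remains.
- The course under continued individual treatment is a coherent target for a trial in this setting. That is so, but the protocol does not declare it as the target, and its primary question is broader.
- Only the protocol was available, and an analysis plan may specify the follow-up analysis. No analysis plan can recover questionnaires that were never sent.

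**Conclusion.** The concern holds in a limited form. Sections 5.2 and 6.6 conflict with sections 6.1.2 and 6.3 and with the Summary, and must be reconciled. Followed as written, the stopping rules lose outcomes after an event that unblinded therapists, and the feedback itself, can influence. The reliance on multilevel analysis does not cover the course after a change of main treatment.

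Size and direction cannot be derived from the document. It might be tempting to put a figure on the lost effect. For instance, 10% to 20% more referrals with a shift of 0.3 to 0.8 SD gives 0.10 × 0.3 = 0.03 to 0.20 × 0.8 = 0.16 SD, or 10% to 53% of 0.30. Those rates are wholly assumed, and the product supposes that nothing after referral is captured, even at follow-up. It is not an estimate. What can be said is that bias arises if exit or its consequences differ by arm, and that it could hide harm as easily as benefit. The matter should be settled in the protocol because outcomes not collected cannot be recovered afterwards.

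**What to change.** Replace section 6.6 and the data-collection stop in section 5.2 (and its repeat in the Summary) with one rule:

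- Every randomised patient who has not withdrawn consent is sent the 3- and 6-month OQ-45 after drop-out, referral or change of main treatment, timed from the end of individual treatment or from study exit.
- Where individual sessions continue, the session OQ-45 continues within the existing limit of 15 sessions or one year. No session measure is asked for once sessions have ended, because it would have no defined timing.
- Date and reason of each exit are recorded.
- Follow-up is analysed by randomised arm, and referral and drop-out are reported by arm.

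Align sections 6.1.2, 6.3 and 6.4 with this rule. Leave the provision in section 6.4 for withdrawal for urgent medical reasons unchanged. The change concerns data collection only and implies nothing about clinical care.

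The cost is an amendment, a sentence in the patient information and a few extra 5-minute questionnaires through the existing web system. The maximum of 17 questionnaires in section 9.3 already equals 15 sessions plus the two follow-ups. Response among drop-outs will be incomplete, so the rule reduces the selection but does not remove it.
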